3.3 Number of subjects/ assignment to treatment groups

A total of 45 neonates and infants will be assigned to study treatment, comprising 3 cohorts to be dosed sequentially in the following order:

Cohort 1: 15 subjects with gestational age ≥ 37 weeks.

Cohort 2: 15 subjects with gestational age 33 to [completed] 36 weeks.

Cohort 3: 15 subjects with gestational age 28 to [completed] 32 weeks.

Cohorts 2 and 3 will be further stratified by post-natal age (≥ 28 days, or < 28 days) so that at least 5 subjects are assigned to study treatment in each group.

The safety data and PK data of the first 3 subjects of Cohort 1 will be reviewed by the investigators and the sponsor's clinical and drug safety representatives prior to dosing of subsequent subjects.

In Cohorts 2 and 3, dosing may not start until at least 5 subjects in the prior cohort have completed dosing as planned, the follow-up safety assessments have been completed, and safety and PK data have been reviewed by the investigators and the sponsor.

The investigators and the sponsor will have regular consultation meetings or tele-conferences to assess the safety and PK data during the course of the study. These meetings to review safety and PK data will be held whenever 5 new subjects (dosed in any cohort) have completed dosing and safety follow-up, and their PK data have been analysed. Consultation meetings may be conducted more frequently if required. Pharmacokinetic analyses will be provided in a timely fashion during the study.

The discussion and consensus decision-making of the consultation meetings between the investigators and the sponsor's clinical and drug safety representatives will be governed by a charter and documented in minutes.

3.4 Centers

This study will be carried out in approximately 8 study centers in Europe, and in 10 centers in the USA. In the event of slow recruitment, additional centers may be considered.

4 STUDY POPULATION

4.1 Target population

The target population comprises male and female neonates and infants aged up to 3 months (inclusive) who are undergoing treatment with systemic antibiotics for documented or presumed bacterial infections, or because they are at risk of infection.

4.2 Inclusion criteria

Subjects must meet all of the following criteria to be assigned to study treatment:

1. Neonates and infants ≤ 3 months, with gestational age ≥ 28 weeks
2. Documented or presumed (or at risk of) bacterial infections, and currently receiving antibiotic treatment*
3. Expected to survive beyond the first 7 days after enrolment
4. Sufficient vascular access to receive study drug, and to allow blood sampling at a site separate from the study drug infusion site
5. Parent's / legally acceptable representative's informed consent to participate in the study

* Subjects must be scheduled to receive at least one infusion of systemic antibiotics before, and at least one infusion after, their ceftobiprole dose.

4.3 Exclusion criteria

Subjects meeting any of the following criteria will be excluded from the study:

1. Major birth defect or malformation syndrome⁺
2. Proven presence of an immunodeficiency
3. HIV or other congenital viral or fungal infection
4. Significant laboratory abnormalities including:
 - Haematocrit < 20%
 - Absolute neutrophil count (ANC) < $0.5 \times 10^9/L$
 - Platelet count < $50 \times 10^9/L$
 - Alanine aminotransferase (ALT), aspartate aminotransferase (AST) > 3 × the age specific upper limit of normal (ULN)
5. Impaired renal function or known significant renal disease, as evidenced by an estimated glomerular filtration rate (using the Schwartz formula or other applicable formula) calculated to be less than 2/3 of normal for the applicable age group[‡]
6. Any condition which would make the subject or caregiver, in the opinion of the investigator, unsuitable for the study

⁺ Subject eligibility will be decided based on an individualized assessment. Subjects with major birth defects or malformation syndromes should be excluded in view of the following

- A low likelihood that the subject will complete the study
- Increased risk of side effects with ceftobiprole (e.g. seizures in patients with CNS disorders)
- An expected impact on pharmacokinetics (e.g., haemodynamically relevant shunts)

[‡] See [Appendix 4](#) for supporting data and the table of GFR thresholds.

4.4 Criteria for premature withdrawal and replacement of subjects

While premature withdrawal is generally not applicable to a single-dose study, the 4-h infusion may be stopped at the investigator's discretion in the event of adverse reactions (including but not limited to allergic-type reactions, infusion site reactions, or clinically relevant changes in vital signs), or in the event of apparent infant distress, or at the request of the parent or the legally acceptable representative.

If the infusion is stopped, the exact time of the termination will be entered into the electronic case report form (eCRF).

Subjects who do not receive the complete infusion may be replaced by enrolment of a new subject meeting the same cohort definitions of gestational and post-natal age (see Section 3.3).

4.5 Concomitant and previous medication and treatment

Each subject will receive treatment with systemic antibiotics (based on clinical grounds) as prescribed by the investigator. Subjects may also receive other medication and treatment, without restriction, at the investigator's discretion.

All medication given to the subject during the course of the study will be entered into the eCRF; information to be recorded will include the trade name of the medication, the indication, the dose and frequency of treatment, and the start and stop dates of treatment. Changes in the dose or schedule of a given medication will also be entered into the eCRF.

Medication given within 7 days before screening up to the start of ceftobiprole dosing will be recorded as prior medication; if given after the start of ceftobiprole dosing, up to the follow-up safety assessment on Day 7±3, it will be recorded as concomitant.

5 SCHEDULE OF ASSESSMENTS AND PROCEDURES

5.1 Summary schedule of assessments

Table 2 presents a summary of the assessments to be performed from screening to the final post-treatment visit.

Table 3 presents a more detailed summary of the assessments and PK sampling times to be performed on Day 1.

5.1.1 Screening (Days -1 to 1)

A parent or legally acceptable representative must provide written informed consent for a subject to participate in the study before any study-specific procedures are carried out.

Informed consent must be obtained within 3 days prior to dosing on Day 1. Once written informed consent is obtained, subjects are considered enrolled in the study.

Subjects in the appropriate Cohort (see Section 3.3) for whom consent has been provided will undergo screening evaluations within 24 hours prior to ceftobiprole dosing. Screening evaluations and dosing may be performed on the same day (Day 1). Laboratory analyses required as part of the screening process which have been performed within the 48 hours prior to ceftobiprole dosing do not need to be repeated, regardless of whether they were performed before or after signing of the ICF.

Screening evaluations (see Table 2) will comprise:

- physical examination
- medical history (within 30 days prior to enrolment)
- review and recording of medication given within the previous 7 days, including systemic antibiotics to be given before and after ceftobiprole dosing
- safety laboratory tests (haematology, clinical chemistry, and urinalysis; see Section 5.2.3.2)
- review of enrolment criteria to ensure subject eligibility, including laboratory test results
- vital signs, body weight and height

Physical examination results and body weight obtained during the screening evaluation do not need to be repeated as Day 1 assessments if they were performed within 6 hours prior to dosing on Day 1.

Table 2 Schedule of assessments

	Screening Day –1 to 1	Dosing Day 1	Follow-up Day 7±3
SCREENING AND ADMINISTRATIVE PROCEDURES			
Written Informed consent ¹	X		
Inclusion/exclusion criteria	X		
Medical history	X		
Prior medications ²	X		
CEFTOBIPROLE ADMINISTRATION			
Infusion of ceftobiprole ³		X	
Collection of aliquot of infusion solution ⁴		X	
PHARMACOKINETIC PROCEDURES			
Blood sample collection ⁵		X	
Urine collection ⁶		X	
SAFETY PROCEDURES			
Vital signs ⁷	X	X	X
Physical examination	X	X*	X
Body weight and height ⁸	X	X*	X
Laboratory tests ⁹	X		X
Concomitant medication		X	X
Adverse events		<----- X ----->	

¹ Informed consent must be obtained within 3 days prior to dosing on Day 1.

² Prior medications administered within the 7 days prior to dosing will be collected.

³ Ceftobiprole must be administered via a separate infusion line. No other intravenous infusion may be given through the same line during the 4-hour ceftobiprole infusion, and – if feasible – attempts should be made to not simultaneously administer any other antibiotic treatment (i.e., through any infusion line) during the ceftobiprole infusion. If feasible, attempts should be made to allow for a minimum period of 30 minutes between the end of administration of any other antibiotic treatment and the start of ceftobiprole medocartil infusion.

⁴ An aliquot of approximately 3 mL of infusion solution will be collected after completion of the ceftobiprole infusion and frozen at below –65 °C immediately after sampling.

⁵ Blood samples of 200–300 µL will be obtained for PK analysis at the times described in [Table 3](#).

⁶ Attempts should be made to obtain urine at the times described in [Table 3](#); **NB**: Full portions of urine will be collected from subjects in whom a urinary catheter has been placed for their standard clinical care. Urinary catheters will not be placed for the purpose of the study. For subjects without a urinary catheter, one or more portions of urine may be obtained before, during, and after dosing.

⁷ Vital signs (body temperature, respiratory rate, pulse rate, and systolic and diastolic blood pressures) will be measured at the times described in [Table 3](#).

⁸ Height must be recorded at screening only. The body weight determination on Day 1 will be used for dose calculation and should be obtained within 6-hours prior to dosing.

⁹ Safety laboratory tests include haematology, biochemistry, and urinalysis (see [Section 5.2.3.2](#)).

*Physical examination and body weight obtained during the screening evaluation do not need to be repeated as Day 1 assessments if they were performed within 6 hours prior to dosing on Day 1.

Table 3 Schedule of PK sampling and vital signs on Day 1

Time	Vital signs	Blood samples	Urine collection*	Infusion solution aliquot collection
-2 to 0 h			X	
-15 min	X			
Pre-dose		X		
0 to 2 h			X	
1 h	X			
2 h		X		
2 h 15 min	X			
2 to 4 h			X	
4 h (end of infusion)		X		X
4 to 8 h			X	
6 h	X	X		
8 h		X		
8 to 12 h			X	
12 h		X		

* NB: Full portions of urine will be collected from subjects in whom a urinary catheter has been placed for their standard clinical care. Urinary catheters will not be placed for the purpose of the study. For subjects without a urinary catheter, one or more portions of urine may be obtained before, during, and after dosing.

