5.1.2 Ceftobiprole dosing (Day 1)

The ceftobiprole dose should be scheduled so that the infusion and subsequent assessments (see [Table 3](#)) do not conflict with the ongoing therapy with systemic antibiotics, or routine care.

Ceftobiprole medocartil must be reconstituted and diluted for intravenous (i.v.) administration as described in Section 6.2. Briefly, a single infusion of ceftobiprole medocartil will be given at 7.5 mg/kg (calculated as ceftobiprole mg equivalents; see Section 6.1), in a weight-adjusted volume of infusion solution given as a constant rate over 4 hours. The date and exact start and stop times of the infusion will be entered into the eCRF.

Ceftobiprole must be administered via a separate infusion line. No other intravenous infusion may be given through the same line during the 4-hour ceftobiprole infusion, and – if feasible – attempts should be made to not simultaneously administer any other antibiotic treatment (i.e., through any infusion line) during the ceftobiprole infusion. If feasible, attempts should be made to allow for a minimum period of 30 minutes between the end of administration of any other antibiotic treatment and the start of ceftobiprole medocartil infusion. Body weight measured on Day 1 will be used for dose calculation and should be obtained within 6 hours prior to dosing.

Blood samples (200–300 µL) and urine (if possible) for PK analysis will be collected and prepared (see Sections 5.2.2.1 and 5.2.2.2, respectively), at times described in Table 3.

A physical examination will be performed on Day 1 and body weight will be obtained, unless physical examination and body weight were obtained during the screening evaluation within 6 hours prior doing on Day 1.

Vital signs will be recorded at times described in Table 3.

After completion of the ceftobiprole infusion, an aliquot of approximately 3 mL of infusion solution will be collected and sent for analysis as described in Appendix 2.

Changes in medication will be recorded. Adverse events will be monitored and recorded continuously throughout the study (see Table 2 and Section 5.2.3.1).

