6 STUDY DRUGS

6.1 Dose and schedule

Subjects will receive a single infusion of ceftobiprole medocartil, given in a weight-adjusted volume at a constant rate over 4 hours. The dose will be 7.5 mg/kg, calculated as ceftobiprole equivalents (7.5 mg ceftobiprole corresponds to 10.0 mg ceftobiprole medocartil sodium).

Ceftobiprole must be administered via a separate infusion line. No other intravenous infusion may be given through the same line during the 4-hour ceftobiprole infusion, and – if feasible – attempts should be made to not simultaneously administer any other antibiotic treatment (i.e., through any infusion line) during the ceftobiprole infusion. If feasible, attempts should be made to allow for a minimum period of 30 minutes between the end of administration of any other antibiotic treatment and the start of ceftobiprole medocartil infusion.

As described in [Section 3.3](#), subjects will be assigned to 3 cohorts on the basis of gestational age, and further stratified by post-natal age. The 3 cohorts will be dosed sequentially. Subjects in Cohorts 2 and 3 may not be dosed until at least 5 subjects from the previous cohort have received their full planned dose and undergone the follow-up safety evaluation (Day 7±3).

Before initiation of dosing in Cohort 2 and Cohort 3, available safety data from subjects in the previous cohort will be made available to all investigators, and the decision to initiate dosing in a new cohort will be made jointly by the sponsor and the investigators.

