⁴ Muller. $\%fT > MIC$ predicts the microbiological eradication at end of treatment with ceftriaxone or ceftobiprole in patients with community acquired pneumonia. ICAAC 2013 Poster A-472

Previous pharmacokinetic and safety results

Experience in adults

The disposition of ceftobiprole is linear in the dose range investigated (from 250 mg to 1000 mg). The half-life is approximately 3 h with limited accumulation after repeated every 8-hour (q8h) administration. The PK are highly reproducible, with a low inter- and intra-subject variability. Ceftobiprole is distributed in the extracellular compartment (18 L), and is weakly bound to plasma proteins (16%). Its elimination is predominantly renal by passive glomerular filtration (>80% of the dose recovered as unchanged drug in urine); creatinine clearance is therefore the main driver of exposure to ceftobiprole.

Ceftobiprole was well tolerated in adult healthy subjects and patients in clinical studies, with the main reported treatment-emergent AEs being dysgeusia, nausea and vomiting. In pooled safety data from two Phase 3 studies in subjects with complicated skin and soft tissue infections (dosing regimens of 500 mg q12h 1-h infusion and 500 mg q8h 2-h infusion), the incidence of these AEs was not related to the dose but was rather related to the infusion duration, suggesting a C_{max} related effect. The dose regimen that was primarily investigated in phase 3 studies in adult subjects with complicated skin and soft tissue infections, community-acquired pneumonia and nosocomial pneumonia was 500 mg q8h as a 2-h infusion. Multiple doses up to 1000 mg q8h as a 1.5-h infusion were also investigated in adult healthy subjects, and were well tolerated.

Experience in juvenile animals

A study was conducted in neonatal and juvenile male and female rats (commencing on post-partum Day 1 up to 50 days, followed by a 28-day recovery period). Exposure to ceftobiprole was determined in each dose group investigated throughout the study. The NOAEL in this study was determined to be 100 mg ceftobiprole medocaril/kg/day [9]. The corresponding exposures are summarized in Table 5.

Table 5 Exposure to ceftobiprole at the NOAEL in juvenile rats

100 mg/kg/day s.c.		Female rats		Male rats	
Study day post-partum	Approximate human equivalent age	C_{max} (µg/mL)	AUC _{0-8h} (µg.h/mL)	C_{max} (µg/mL)	AUC _{0-8h} (µg.h/mL)
Day 1	neonate	65.9	261	55.7	265
Day 18	~ 6 years	101	133	92.6	148
Day 49	~ 14 years	84.0	119	76.1	139

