⁹ Safety laboratory tests include hematology, biochemistry, and urinalysis (see protocol Section 5.2.3.2).

*Physical examination and body weight obtained during the screening evaluation do not need to be repeated as Day 1 assessments if they were performed within 6 hours prior to dosing on Day 1.

The schedule of PK sampling and vital signs on Day 1 are summarized in Table 2 below:

Table 2: Schedule of PK sampling and vital signs on Day 1

Time	Vital signs	Blood samples	Urine collection *	Infusion solution aliquot collection
-2 to 0 h			X	
-15 min	X			
Pre-dose		X		
0 to 2 h			X	
1 h	X			
2 h		X		
2 h 15 min	X			
2 to 4 h			X	
4 h (end of infusion)		X		X
4 to 8 h			X	
6 h	X	X		
8 h		X		
8 to 12 h			X	
12 h		X		

* **NB:** Full portions of urine will be collected from subjects in whom a urinary catheter has been placed for their standard clinical care. Urinary catheters will not be placed for the purpose of the study. For subjects without a urinary catheter, one or more portions of urine may be obtained before, during, and after dosing.

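### No vital signs are scheduled at the end of the 4-hour infusion, so vital-sign changes at peak exposure cannot be tabulated or paired with the 4 h concentration

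*Protocol*

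**What the plan says.** The Day 1 times are in Protocol Table 3, titled "Schedule of PK sampling and vital signs on Day 1". Its vital-signs column is marked at -15 min, 1 h, 2 h 15 min and 6 h. The row labelled "4 h (end of infusion" is marked for a blood sample and for the infusion-solution aliquot, and its vital-signs cell is empty.

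No other text adds a reading. Protocol 5.1.2 states that "Vital signs will be recorded at times described in Table 3". Footnote 7 to Table 2 also defers to Table 3, and section 5.2.3.4 refers back to Tables 2 and 3. SAP 2.4 reproduces the same grid ("The schedule of PK sampling and vital signs on Day 1 are summarized in Table 2 below"), with the same empty cell.

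The drug is "given in a weight-adjusted volume at a constant rate over 4 hours" (Protocol 6.1). SAP 5.7 summarises actual vital-sign values, changes from baseline and marked changes. SAP section 5 says that unscheduled assessments are listed only, unless otherwise specified, and SAP 5.7 makes no exception.

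**The concern.** Safety and tolerability is the secondary objective, and vital signs are one of its named assessments. With a constant-rate infusion, plasma concentration rises until the pump stops, so the highest exposure is expected at 4 h. That is also when the concentration is measured. Without blood pressure, pulse, respiration and temperature at that time, the vital-sign tables cannot show what happened at peak exposure, and no infant's reading can be set beside the concentration at the end of infusion.

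A reading taken at 4 h on local initiative would appear in a listing but not in the SAP 5.7 summaries. The reviews in Protocol 3.3, of the first 3 infants and then of at least 5 before each later cohort, would likewise have no scheduled vital signs at the peak.

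**Working it through.** **Reading the schedule.** The last scheduled reading before the end of infusion is at 2.25 h and the next is at 6 h. The gap is 6 - 2.25 = 3.75 h: the last 4 - 2.25 = 1.75 h of the infusion and the first 2 h after it. Protocol Table 3 and SAP Table 2 agree on this.

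**Inputs.** The infusion lasts 4 h at a constant rate (Protocol 6.1). The half-lives come from Appendix 1, Table 8: 1.6 to 2.3 h under normal conditions and 9 to 11 h in the worst case. The documents give no predicted concentration at the reading times, so there is no such figure to reproduce. Table 8 does print a dose rate, and dose divided by 4 h gives 6.42, 6.85, 7.62, 9.43 and 11.0 mg/h against the printed 6.4, 6.9, 7.6, 9.4 and 11.0. Table 8 therefore rests on the same 4-hour infusion.

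**Model (my assumption: one compartment).** With k = ln 2 / half-life:

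- during the infusion, C(t)/C(4) = (1 - e^(-kt)) / (1 - e^(-4k));
- after the infusion, C(t)/C(4) = e^(-k(t - 4)).

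The ratio depends on the half-life only; dose and clearance cancel.

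**Worked example, half-life 2.3 h.** k = 0.693/2.3 = 0.301 per hour.

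- 2.25 h: (1 - 0.508)/(1 - 0.300) = 0.70.
- 6 h: e^(-0.603) = 0.55.

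**Predicted concentration as a share of the 4 h peak**

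| Half-life (h) | Source | 1 h | 2 h 15 min | 6 h |
|---|---|---|---|---|
| 1.6 | Table 8, normal | 43% | 76% | 42% |
| 1.9 | Table 8, normal | 40% | 73% | 48% |
| 2.2 | Table 8, normal | 38% | 71% | 53% |
| 2.3 | Table 8, normal | 37% | 70% | 55% |
| 3 | sensitivity | 34% | 67% | 63% |
| 3.5 | sensitivity | 33% | 66% | 67% |
| 4 | sensitivity | 32% | 65% | 71% |
| 9 | Table 8, worst case | 28% | 60% | 86% |
| 10 | Table 8, worst case | 28% | 60% | 87% |
| 11 | Table 8, worst case | 27% | 59% | 88% |

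With normal elimination the best-placed scheduled reading is the one at 2 h 15 min, at 70-76% of peak. In the worst case it is the one at 6 h, at 86-88%. Between these, at the 3 to 4 h half-life that Protocol 1.2.2.1 gives for adults, the best-placed reading is at about 67-71% of peak.

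**The case against.** A reader might infer that the safety data as a whole miss the peak, and that this is the peak Appendix 1 holds responsible for adverse effects. The documents do not support that, for two reasons.

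- Adverse events are recorded continuously from the start of study drug (Protocol 5.1.2 and 5.2.3.1), and each infant is directly observed during the infusion (Protocol 6.5, stated for compliance). Only the scheduled vital signs miss the peak.
- The Appendix 1 remark that incidence "was not related to the dose but was rather related to the infusion duration, suggesting a C_{max} related effect" concerns dysgeusia, nausea and vomiting in adults given 1-hour or 2-hour infusions. It names no change in blood pressure, pulse, respiration or temperature. Vital signs at 4 h would not detect those effects, and the remark gives no reason to predict a vital-sign change at the peak.

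A reader might also cite Protocol 4.4, which allows the infusion to be stopped for "allergic-type reactions, infusion site reactions, or clinically relevant changes in vital signs". That does not argue for a 4 h reading, since by then no infusion is left to stop.

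Three further points against the concern have force. Infants with slow elimination, who have the highest predicted AUC in Table 8 (157.1 to 189.8 against 42.8 to 63.2 µg·h/mL), do have a scheduled reading near the peak, at 6 h. The analysis is descriptive and uncontrolled, and these infants are receiving other antibiotics, so one more mean and SD would do little to attribute a change to the drug. The SAP also reports that only Cohort 1 was completed, so editing SAP Table 2 cannot create readings.

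These points limit the weight of the concern. They do not supply the missing measurement: the gap is real, no text explains it, and the SAP rule on unscheduled readings prevents the tables from filling it.

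**Conclusion.** The point holds in a limited form. No vital signs are scheduled between 2 h 15 min and 6 h, so vital-sign changes at the expected Cmax can be neither summarised nor paired with the 4 h concentration. The best-placed scheduled reading is at about 70-76% of peak with normal elimination and about 86-88% in the worst case. The gap therefore matters mainly for infants who clear the drug at the normal or an intermediate rate.

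The percentages rest on a one-compartment model, a full 4-hour infusion and the Table 8 half-lives. The smallest dose in Table 8, 25.7 mg, corresponds to 25.7/7.5 = 3.4 kg, so those half-lives may not describe small preterm infants. The empty 4 h cell and the 3.75 h gap depend on none of this.

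The primary pharmacokinetic objective is unaffected. This is a low-cost improvement to the secondary safety objective. It is not evidence that a safety signal was missed.

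**What to change.** In Protocol Table 3, and in any SAP table that repeats it, mark vital signs in the 4 h row, to be taken at the contact already planned for the blood sample and the aliquot. Keep the 2 h 15 min reading. Moving it to 4 h would leave 1 h as the only scheduled reading between the start and the end of the infusion.

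This can apply only to infants still to be dosed or to a successor protocol. For data already collected, the report should state that no vital signs were scheduled between 2 h 15 min and 6 h, and that the vital-sign tables therefore do not describe the end of infusion.

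The cost is one extra routine, non-invasive set of readings per infant, with no extra blood and no extra staff contact. For existing data it is a sentence in the report.
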